## List of Acronyms and Abbreviations

Acronym/ Abbreviation	Expanded Term
AAD	Antiarrhythmic Drug
ACC/AHA	American College of Cardiology/American Heart Association
ACE	Asymptomatic Cerebral Embolic
ACL	Advanced Catheter Location
ACT	Activated Clotting Time
AE	Adverse Event
AEF	Atrioesophageal Fistula
AF	Atrial Fibrillation
AFEQT™	Atrial Fibrillation Effect on Quality-of-Life
AFL	Atrial Flutter
APHRS	Asia Pacific Heart Rhythm Society
AT	Atrial Tachycardia
AV	Atrioventricular
CB-2	Second-Generation Cryoballoon
CEC	Clinical Events Committee
CHF	Congestive Heart Failure
CPK	Creatine Phosphokinase
COPD	Chronic Obstructive Pulmonary Disease
CRF	Case Report Form
CS	Coronary Sinus
CT	Computed Tomography
CTI	Cavo-Tricuspid Isthmus
CVA	Cerebrovascular Accident or Stroke
DC	Direct Current
DMC	Data Monitoring Committee
EC	Ethics Committee
ECAS	European Cardiac Arrhythmia Society
ECG	Electrocardiogram
eCRF	Electronic Case Report Form
EDC	Electronic Data Capture
EHRA	European Heart Rhythm Association
EMEA	Europe, Middle East and Africa
EP	Electrophysiology
ESC	European Society of Cardiology
FAM	Fast Anatomical Mapping
FDA	Food and Drug Administration
F	French
FU	Follow-Up
GCP	Good Clinical Practices
HB	Hot Balloon
HRS	Heart Rhythm Society
ICD	Implantable Cardioverter Defibrillator
ICE	Intracardiac Echocardiography
ICF	Informed Consent Form
ICH	International Conference on Harmonization
ICL	Independent Current Location
IFU	Instruction for Use

Acronym/ Abbreviation	Expanded Term
IRB	Institutional Review Board
LA	Left Atrium
LB	Laser Balloon
LV	Left Ventricle
LVEF	Left Ventricular Ejection Fraction
MDR	Medical Device Regulation
MEDDEV	Medical Device Directive Guidance
MI	Myocardial Infarction
mITT	Modified Intention to Treat
MMSE	Mini-Mental State Examination
MoH	Ministry of Health
MRA	Magnetic Resonance Angiogram
MRI	Magnetic Resonance Imaging
mRS	Modified Rankin Scale
NAE	Neurological Assessment Evaluable
NIHSS	National Institutes of Health Stroke Scale
NMPA	National Medical Products Administration
NYHA	New York Heart Association
OUS	Outside the United States
PAE	Primary Adverse Event
PAF	Paroxysmal Atrial Fibrillation
PI	Principal Investigator
PN	Phrenic Nerve
PNP	Phrenic Nerve Palsy
PV	Pulmonary Vein
PVI	Pulmonary Vein Isolation
QoL	Quality of Life
RA	Right Atrium
RF	Radiofrequency
RSPV	Right Superior Pulmonary Vein
RV	Right Ventricle
SAE	Serious Adverse Event
SADE	Serious Adverse Device Effect
SAP	Statistical Analysis Plan
SOLAECE	Latin American Society of Electrophysiology and Cardiac Stimulation
TEE	Transesophageal Echocardiography
TIA	Transient Ischemic Attack
TS	Transseptal
TTE	Transthoracic Echocardiography
TTM	Transtelephonic Monitoring
UADE	Unanticipated Adverse Device Effect
US	United States
USADE	Unanticipated Serious Adverse Device Effect

## Protocol Summary

**Study Name:** STELLAR

**Study Title:** Safety and Effectiveness Evaluation of the Multi-Electrode Radiofrequency Balloon Catheter for the Treatment of Symptomatic Paroxysmal Atrial Fibrillation.

**Study Number:** BWI\_2017\_04

**Study Description:** This clinical study is a prospective, multicenter, single-arm clinical evaluation of the Multi-Electrode Radiofrequency (RF) Balloon catheter (HELIOSTAR™). The purpose of this study is to evaluate the overall safety and effectiveness of the HELIOSTAR™ catheter, in conjunction with the Multi-Electrode Circular Diagnostic catheter (LassoStar™) and Multi-Channel RF Generator, for the treatment of drug refractory Paroxysmal Atrial Fibrillation (PAF). Embedded within the Main Study will be a Neurological Assessment Evaluable (NAE) subset and a Cardiac Computed Tomography (CT) or Magnetic Resonance Angiogram (MRA) image (CT/MRA) subset with consecutive enrollment and a prospective design. The same subject can participate in both the NAE and cardiac CT/MRA subsets.

The study will enroll subjects with drug refractory, symptomatic PAF who are candidates for catheter ablation. The first 1-3 subjects for each ablating physician will be considered roll-in subjects to verify consistent workflow for study device components and to minimize any learning curve effects. The roll-in subjects will not be included in the NAE subset, cardiac CT/MRA subset, or in the primary endpoint analyses. The roll-in phase will include a maximum of 240 subjects and the main study phase will include a maximum of 400 evaluable subjects. Subjects will be evaluated prior to the procedure, prior to discharge, and post procedure at 7 days (7-14 days), 1 month (23-37 days), 3 months (76-104 days), 6 months (150-210 days), and 12 months (315-405 days) unless otherwise specified in the protocol.

**Objective:** **Primary Objective:**

To demonstrate the safety and 12-month effectiveness of the HELIOSTAR™ catheter for the treatment of drug refractory PAF. Specifically:

- To demonstrate the safety based on the incidence of early-onset (within 7 days of ablation procedure) primary adverse events.
- To demonstrate the 12-month effectiveness based on the proportion of subjects with freedom from documented asymptomatic and symptomatic Atrial Fibrillation (AF), Atrial Tachycardia (AT), or Atrial Flutter (AFL, of unknown origin\*) episodes based on electrocardiographic data through the effectiveness evaluation period (day 91-365 post index procedure).

\*AFL of unknown origin is defined as all AFL except those cavo-tricuspid isthmus (CTI) dependent AFL as confirmed by accepted EP maneuvers (e.g. entrainment or activation mapping) in an EP study

### Secondary Objectives:

- To determine the acute procedural success, defined as confirmation of entrance block in clinically relevant pulmonary veins (all pulmonary veins except those that are silent and/or cannot be cannulated) after adenosine and/or isoproterenol challenge, of the HELIOSTAR™ catheter (with or without the use of a focal catheter).
- To demonstrate the 12-month effectiveness based on freedom from documented symptomatic AF/AT/AFL (of unknown origin) episodes based on electrocardiographic data through the effectiveness evaluation period.
- To evaluate treatment success for subjects treated with the HELIOSTAR™ catheter including subjects who were taking antiarrhythmic drug (AAD) medication past the blanking period.
- To determine the single procedure treatment success rate for subjects treated with the HELIOSTAR™ catheter.
- To assess subject quality of life at 12 months compared to baseline, via the Atrial Fibrillation Effect on Quality-of-Life (AFEQT™) Questionnaire, for subjects treated with the HELIOSTAR™ catheter.

### Endpoint:

#### Primary Endpoints:

- **Safety**

Incidence of early onset Primary Adverse Events (PAEs) (within 7 days of an ablation procedure which uses the HELIOSTAR™ catheter). PAEs include the following adverse events (AEs) and are defined in section 9.2.3 of the protocol:

- Device or procedure related death\*
- Atrio-Esophageal Fistula\*
- Myocardial Infarction
- Cardiac Tamponade/Perforation\*
- Thromboembolism
- Stroke/ Cerebrovascular Accident (CVA)
- Transient Ischemic Attack (TIA)
- Phrenic Nerve Paralysis (permanent)
- Pulmonary Vein Stenosis\*
- Pericarditis
- Pulmonary Edema
- Major Vascular Access Complication/Bleeding
- Hospitalization (initial or prolonged)\*\*

\* Events are considered and analyzed as primary AEs **even if they occur greater than one week (7 days) post-procedure.**

\*\* Excludes hospitalization solely due to arrhythmia recurrence or non-medically urgent cardioversion.

- **Effectiveness**

Freedom from documented asymptomatic and symptomatic Atrial Fibrillation, Atrial Tachycardia, or Atrial Flutter of unknown origin+ episodes based on electrocardiographic data (≥30 seconds on arrhythmia

monitoring device) through the effectiveness evaluation period (91-365 days post index procedure). Additionally, if a subject meets any one of the following criteria, then the subject will be considered an effectiveness failure:

- Failure to achieve acute procedural success. Acute procedural success is defined as confirmation of entrance block in clinically relevant PVs (all PVs except those that are silent and/or cannot be cannulated) after adenosine and/or isoproterenol challenge (with or without the use of a focal catheter).
- Greater than 2 repeat ablations for AF/AT/AFL (of unknown origin\*) in the blanking period ( $\leq 90$  days post index procedure) or a repeat ablation or surgical treatment for AF/AT/AFL (of unknown origin\*) during the effectiveness evaluation period.
- Direct current (DC) cardioversion for AF/AT/AFL (of unknown origin\*) during the effectiveness evaluation period.
- Continuous AF/AT/AFL (except CTI dependent) on a standard 12-lead ECG during the effectiveness evaluation period.
- A Class I and/or Class III AAD is prescribed/taken for atrial arrhythmia other than CTI dependent AFL at any time beyond the 3-month follow-up visit window (i.e., at any time beyond day 105 to 365 post index procedure).
- Oral Amiodarone is prescribed post index ablation procedure.
- Failure to use the HELIOSTAR™ catheter for isolation of clinically relevant PVs (all PVs except those that are silent and/or cannot be cannulated) in the index procedure or repeat procedures during the blanking period.

\*AFL of unknown origin is defined as all AFL except those CTI dependent AFL as confirmed by accepted EP maneuvers (e.g. entrainment or activation mapping) in an EP study.

### Secondary Endpoints:

- Acute procedural success defined as confirmation of entrance block in clinically relevant PVs (all PVs except those that are silent and/or cannot be cannulated) after adenosine and/or isoproterenol challenge (with or without the use of a focal catheter).
- Alternative 12 Month Success: Defined as acute procedural success and freedom from documented symptomatic AF/AT/AFL (of unknown origin) episodes based on electrocardiographic data ( $\geq 30$  seconds on arrhythmia monitoring device) through the effectiveness evaluation period. Greater than 2 repeat ablations for AF/AT/AFL (of unknown origin) in the blanking period, a repeat ablation or surgical treatment for AF during the effectiveness evaluation period, DC Cardioversion during the effectiveness evaluation period, Continuous AF/AT/AFL (except CTI dependent) on a standard 12-lead ECG during the effectiveness evaluation period, class I and/or III AAD usage at any time beyond the 3-month follow-up visit window (i.e., at any time from day 105 to 365 post index procedure), oral Amiodarone usage after the index procedure, or failure to use the HELIOSTAR™ catheter for isolation of clinically relevant

[figure not shown]
PVs (all PVs except those that are silent and/or cannot be cannulated) in the index procedure or repeat procedures during the blanking period constitutes treatment failure.

- 12 Month Symptomatic Recurrence Endpoint: Defined as acute procedural success and freedom from documented symptomatic AF/AT/AFL (of unknown origin) episodes based on electrocardiographic data ( $\geq 30$  seconds on arrhythmia monitoring device) through the effectiveness evaluation period. Any AAD use throughout the study period will not be considered an effectiveness failure. Greater than 2 repeat ablations for AF/AT/ AFL (of unknown origin) in the blanking period, a repeat ablation or surgical treatment for AF during the effectiveness evaluation period, DC Cardioversion during the effectiveness evaluation period, Continuous AF/AT/ AFL (except CTI dependent) on a standard 12-lead ECG during the effectiveness evaluation period, or failure to use the HELIOSTAR™ catheter for isolation of clinically relevant PVs (all PVs except those that are silent and/or cannot be cannulated) in the index procedure or repeat procedures during the blanking period constitutes treatment failure.
- Quality of life at 12 months compared to baseline as assessed by pre and post ablation AFEQT™ Questionnaire.
- 12 Month Single Procedure Treatment Success: Defined as acute procedural success and freedom from documented symptomatic AF/AT/AFL (of unknown origin) episodes based on electrocardiographic data ( $\geq 30$  seconds on arrhythmia monitoring device) through the effectiveness evaluation period. Repeat ablation or surgical treatment for AF at any time, DC Cardioversion during the effectiveness evaluation period, Continuous AF/AT/ AFL (except CTI dependent) on a standard 12-lead ECG during the effectiveness evaluation period, class I and/or III AAD usage at any time beyond the 3-month follow-up visit window (i.e., at any time from day 105 to 365 post index procedure), oral Amiodarone usage after the index procedure, or failure to use the HELIOSTAR™ catheter for isolation of clinically relevant PVs (all PVs except those that are silent and/or cannot be cannulated) in the index procedure constitutes treatment failure.

**Population:** Patients undergoing catheter ablation for the treatment of drug refractory symptomatic PAF.

**Phase:** Pivotal

**Clinical Sites:** Up to 40 clinical sites in the United States (US) and outside the United States (OUS).

**Study Duration:** The study duration is anticipated to be approximately 3.5 years; 2.5 years for the enrollment phase and an additional 1 year to complete follow-up.

**Subject Study Duration:** Enrolled subjects who undergo the ablation procedure with the investigational device will be followed for 12 months post index procedure.

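### Single Procedure Treatment Success names only repeat ablation for AF as a failure, so a blanking-period repeat for AT or non-CTI flutter can count as a single-procedure success

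*Protocol*

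**What the plan says.** All of this is in the Protocol Summary, under Endpoint.

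- **Primary effectiveness.** In days 91-365 a subject fails for "a repeat ablation or surgical treatment for AF/AT/AFL" of unknown origin. In the blanking period (90 days or less) more than two such repeats are a failure. Cardioversion is tied to an indication: "Direct current (DC) cardioversion for AF/AT/AFL" of unknown origin, in the evaluation period.
- **Alternative 12 Month Success and 12 Month Symptomatic Recurrence.** Both keep the wide arrhythmia list for blanking: "Greater than 2 repeat ablations for AF/AT/AFL (of unknown origin) in the blanking period". For the evaluation period both narrow it: "a repeat ablation or surgical treatment for AF during the effectiveness evaluation period". Cardioversion in that period is a failure with no indication given.
- **12 Month Single Procedure Treatment Success.** There is one repeat-treatment rule and no separate blanking rule: "Repeat ablation or surgical treatment for AF at any time, DC Cardioversion during the effectiveness evaluation period". Again, cardioversion has no stated indication.

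All three secondary endpoints also require "freedom from documented symptomatic AF/AT/AFL (of unknown origin) episodes based on electrocardiographic data" through the evaluation period, and all three fail continuous AF/AT/AFL (except CTI dependent) "on a standard 12-lead ECG during the effectiveness evaluation period".

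AFL of unknown origin means all AFL except CTI-dependent AFL confirmed in an EP study.

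**The concern.** The stated secondary objective is a single-procedure success rate. A second ablation in the blanking period is tolerated by the primary and by the other two symptomatic endpoints, which fail only on a third or later repeat. Single Procedure Treatment Success is therefore the one endpoint whose task is to catch a single early repeat. If it catches only repeats done for AF, it misses early repeats for AT or left atrial flutter.

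Those repeats are foreseeable from the protocol itself. Section 9.2.1 treats new left atrial flutter after ablation as an adverse event, and Table 9.3.4A lists atypical left atrial flutter as anticipated. Section 8.5 requires the study device for blanking repeats only when the arrhythmia comes from PV triggers, so repeats for other causes are contemplated.

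At stake is the meaning of one reported secondary rate, and whether two programmers would classify the same subject alike.

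**Working it through.** The plan states no figure on this point, so the check compares the rules on hypothetical subjects. Each is assumed to have acute procedural success, to meet the study-catheter clause, and to have no disqualifying drug use. Apart from the event named, none has a documented symptomatic episode, cardioversion or continuous arrhythmia on ECG in days 91-365.

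The repeat-ablation phrase in the secondary endpoints can be read in two ways. **R1**: repeat ablation for AF, or surgery for AF. **R2**: any repeat ablation, or surgery for AF.

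| Subject | Primary | Alternative and Symptomatic Recurrence | Single Procedure |
|---|---|---|---|
| A. One blanking repeat for AT or non-CTI AFL | not failed | not failed | R1 not failed; R2 failed |
| B. Three blanking repeats for AT | failed | failed | R1 not failed; R2 failed |
| C. Repeat in days 91-365 for AT or non-CTI AFL | failed | R1 not failed; R2 failed | R1 not failed; R2 failed |
| D. Repeat in days 91-365 for CTI-dependent AFL | not failed | R1 not failed; R2 failed | R1 not failed; R2 failed |
| E. Cardioversion in days 91-365 for CTI-dependent AFL | not failed | failed | failed |

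**Blanking period (A, B).** Under R1 nothing else in the single-procedure definition catches A. Its symptomatic-episode, cardioversion and ECG rules run only in the evaluation period. Oral amiodarone at any time after the index procedure would catch some such subjects, but not all. Subject B is the sharpest case: four procedures in total, a failure on the other three endpoints, and a single-procedure success.

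**Days 91-365 (C).** A subject re-ablated for AT or non-CTI AFL in this period normally has a documented arrhythmia. To be counted a success, that subject must have no documented symptomatic episode of 30 seconds or more, no cardioversion and no continuous arrhythmia on a 12-lead ECG. In two of the three endpoints, late Class I/III drug use must also be absent. The gap exists but is narrow.

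**Which reading.** The primary attaches its indication to repeat ablation and surgery together, so the parallel secondary phrase most naturally does the same (R1). The protocol also does not use AF as plain shorthand. The Alternative and Symptomatic Recurrence definitions use both AF/AT/AFL and AF in the same sentence, and section 9.2.1 separates re-ablation for AF from re-ablation for pre-existing AFL or AT.

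**Size.** Let *f* be the share of subjects re-ablated for AT or non-CTI AFL who meet no other failure criterion. Under R1 the single-procedure rate exceeds the rate under an AF/AT/AFL rule by exactly *f*. The documents give no value for *f*. Assumed values, on the maximum of 400 evaluable subjects (SAP section 1):

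- *f* = 1%: 0.01 × 400 = 4 subjects, +1 point
- *f* = 3%: 0.03 × 400 = 12 subjects, +3 points
- *f* = 5%: 0.05 × 400 = 20 subjects, +5 points

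The sample size is adaptive, so 400 is a ceiling. The point difference depends only on *f*.

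**The case against.** The best counter-argument is that R2 was intended. The name and the objective both say single procedure. In addition, the study-catheter clause of this endpoint mentions only the index procedure, whereas the other two endpoints also mention blanking repeats. That omission makes sense if the drafter took any repeat as already a failure. This is a fair argument and makes the text ambiguous. It does not remove the problem: under R2 a repeat for CTI-dependent flutter fails the secondary endpoints but not the primary (subject D), and the two readings still classify subjects A to D differently.

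It is also fair that only the Summary can be read here. Section 3.2.3 appears in the contents, but its text and most of the SAP are not in the public copy. They may settle the point, though the Summary would still have to agree with them.

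A reader might infer more than the documents support:

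- That all three secondary endpoints ignore repeats for AT and AFL. Two of them count more than two blanking repeats for AF/AT/AFL.
- That any flutter is at issue. CTI-dependent AFL is exempt by design, even in the primary.
- That the secondary rates cannot be compared with the primary because of this wording. They already differ by design, since they count only symptomatic episodes and one disregards AAD use.

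**Conclusion.** The point holds for Single Procedure Treatment Success, chiefly in the blanking period. On the natural reading, a repeat for AT or non-CTI AFL does not fail the endpoint, contrary to its name and objective. For the other two endpoints it holds only for repeats in days 91-365, where the practical effect should be small.

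A reader might conclude that the reported rate is inflated by a known amount. The documents do not show that. The direction follows from R1, but the size depends on an unstated rate, and the 1 to 5 points above are illustrations.

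The cardioversion mismatch (subject E) is separate and runs the other way: as written, the secondary endpoints are stricter than the primary.

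The conclusion rests on R1 and on the visible Summary text. No effect on the primary endpoint, alpha or sample size is shown.

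**What to change.** 1. In Single Procedure Treatment Success, make the repeat-ablation and surgery rule apply to AF/AT/AFL (of unknown origin) at any time.
2. In Alternative 12 Month Success and 12 Month Symptomatic Recurrence, use AF/AT/AFL (of unknown origin) in the evaluation-period repeat-ablation clause.
3. If AF only, or any repeat whatever its indication, is what the sponsor intends, say so explicitly. Under change 1 a repeat for CTI-dependent AFL still does not fail the single-procedure endpoint. That matches the primary but should be a stated choice.
4. Reconcile the cardioversion wording between primary and secondary endpoints, or state that the difference is intended.
5. Make section 3.2.3 and the SAP agree with the Summary.

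The cost is wording and programming. Section 8.6 already has every ablation after the index procedure recorded, so no new visit or test is needed; the arrhythmia treated at each repeat must be available to the programmer. Relative to R1, changes 1 and 2 can only lower the success rates, probably slightly. Aligning cardioversion with the primary can only raise them.

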**Study Inclusion criteria:**

1. Diagnosed with Symptomatic PAF (Physician's note indicating recurrent self-terminating AF).
  - a) At least two (2) symptomatic AF episodes within last six (6) months from enrollment.
  - b) At least one (1) electrocardiographically documented AF episode within twelve (12) months prior to enrollment. Electrocardiographic documentation may include, but is not limited to, electrocardiogram (ECG), Holter monitor, or telemetry strip.
2. Failed at least one (1) Class I or Class III AAD as evidenced by recurrent symptomatic AF, contraindication to the AAD, or intolerable side effects to the AAD.
3. Age 18 -75 years.
4. Able and willing to comply with all pre-procedure, post-procedure, and follow-up testing and visit requirements.
5. Signed Patient Informed Consent Form (ICF).

**Study Exclusion criteria:**

1. AF secondary to electrolyte imbalance, thyroid disease, or reversible or non-cardiac cause (e.g. documented obstructive sleep apnea and acute alcohol toxicity).
2. Previous surgical or catheter ablation for AF.
3. Patients known to require ablation outside the PV ostia and CTI region (e.g. atrioventricular reentrant tachycardia, atrioventricular nodal reentry tachycardia, atrial tachycardia, ventricular tachycardia and Wolff-Parkinson-White).
4. Previously diagnosed with persistent or long-standing persistent AF and/or Continuous AF > 7 days.
5. Any percutaneous coronary intervention within the past 2 months.
6. Valve repair or replacement or presence of a prosthetic valve.
7. Any carotid stenting or endarterectomy within the past 6 months.
8. Coronary artery bypass grafting, cardiac surgery (e.g., ventriculotomy, atriotomy), or valvular cardiac surgical procedure within the past 6 months.
9. Documented left atrium (LA) thrombus within 1 day prior to the index procedure.
10. LA antero posterior diameter > 50 mm.
11. Left Ventricular Ejection Fraction (LVEF) < 40%.

12. Contraindication to anticoagulation (e.g., heparin).
13. History of blood clotting or bleeding abnormalities.
14. Myocardial infarction within the past 2 months.
15. Documented thromboembolic event (including transient ischemic attack) within the past 12 months.
16. Rheumatic Heart Disease.
17. Uncontrolled heart failure or New York Heart Association (NYHA) function class III or IV.
18. Awaiting cardiac transplantation or other cardiac surgery within the next 12 months.
19. Unstable angina.
20. Acute illness or active systemic infection or sepsis.
21. Diagnosed atrial myxoma or presence of an interatrial baffle or patch.
22. Presence of implanted pacemaker or implantable cardioverter defibrillator (ICD).
23. Significant pulmonary disease, (e.g., restrictive pulmonary disease, constrictive or chronic obstructive pulmonary disease) or any other disease or malfunction of the lungs or respiratory system that produces chronic symptoms.
24. Significant congenital anomaly or medical problem that, in the opinion of the investigator, would preclude enrollment in this study.
25. Women who are pregnant (as evidenced by pregnancy test if pre-menopausal), lactating, or who are of child bearing age and plan on becoming pregnant during the course of the clinical investigation.
26. Enrolled in an investigational study evaluating another device, biologic, or drug.
27. Has known pulmonary vein stenosis.
28. Presence of intramural thrombus, tumor or other abnormality that precludes vascular access, or manipulation of the catheter.
29. Presence of an inferior vena cava filter.
30. Presence of a condition that precludes vascular access.
31. Life expectancy or other disease processes likely to limit survival to less than 12 months.
32. Presenting contra-indication for the devices (e.g., TTE, Holter, CT, etc.) used in the study, as indicated in the respective instructions for use.

